8.4 Endpoints

8.4.1 Primary Safety Endpoint

The primary safety endpoint is the incidence of serious adverse device effects (SADE), as that term is defined in Section 15.

8.4.2 Primary Efficacy Endpoint

The primary efficacy endpoints are the mechanical ventilation time and proportion of patients successfully weaned at 48- and 120-hours post-op. These will each be evaluated separately for efficacy. A wean will be considered successful if the patient is not reintubated within 48 hours of extubation. The mechanical ventilation time will be the cumulative proportion of time on mechanical ventilation over the 48- or 120-hour period from the entry to the ICU (recorded as ICU Admit Time on the procedure information case report form). If an extubation is attempted but is not successful (i.e., less than 48 hours) then that time will not be considered off of mechanical ventilation. The proportion weaned will be derived from the cumulative incidence function (CIF) of a competing risk analysis.

Data will be analyzed for all patients and using a predictive enrichment threshold of patients on mechanical ventilation. The enrichment strategy is applied to identify patients that may more likely respond to TransAeris stimulation and decrease variability, as per FDA guidance.(14) As the TransAeris treatment is not intended to produce immediate results, but rather is intended to prevent or treat VIDD, patients that are on MV for short periods are expected to have improved spontaneously and thus increase the variability in the outcome measures if included in analysis. Similarly, patients, during the initial hours of mechanical ventilation with paralytic anesthesia still impacting contraction, are not expected to respond to the treatment and thus excluding patients that are weaned from mechanical ventilation during the initial 10 hours post-op will be considered as not part of the predictive enrichment analysis. The data will be considered non-proportional and will be assessed using non-parametric techniques.

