3.6 Description of Investigational Device

3.6.1 *Introduction*

See User Manuals REF 77-1000-FR_B & REF 77-1002-FR_C for complete device instructions.

The TransAeris System is a temporary percutaneous intramuscular diaphragm stimulator intended for patients at risk of or on prolonged positive pressure mechanical ventilation (MV). TransAeris is indicated for use in the prevention and treatment of ventilator-induced diaphragm dysfunction (VIDD).

The TransAeris System includes four TransLoc® intramuscular diaphragm electrodes, the TransAeris external stimulator, and the FrictionLoc® connectors which provide the interface between the TransLoc electrodes and the TransAeris stimulator. Placement of the diaphragm electrodes can be performed in conjunction with another surgical procedure or as the primary procedure. TransAeris is used to provide neuromuscular electrical stimulation to the diaphragm while the patient is on mechanical ventilation to prevent, slow, or reverse diaphragm disuse atrophy and, more generally, to treat VIDD. Once the patient is successfully liberated from mechanical ventilation for 48 hours, the electrodes can be removed from the patient.

A cornerstone of the rationale and evidence supporting the use of intramuscular diaphragm stimulation in the treatment of VIDD comes from the clinical experience with Synapse's NeuRx DPS® (IDE (investigational device exemption) G920162, HDE (humanitarian device exemption) H070003). Patients who have been ventilator dependent for months to years due to chronic high-level spinal cord injury (SCI) have undergone a regimen of diaphragm stimulation with the permanently implanted NeuRx DPS to reverse disuse atrophy and re-educate the muscle. Although diaphragm dysfunction was advanced having accrued over months to years, diaphragm function was substantially restored after just a few days of reconditioning with intramuscular diaphragm stimulation.

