7.5.1.4 Competing Events

At any point during the study both groups will be monitored for competing events that preclude or impede the progression of weaning, i.e. causes other than VIDD that are the source of an inability to wean. These are typically adverse events, unrelated to the device or procedure that will also be recorded in detail, as per Section 15. Identification as a competing event, with time and date of the event, will establish the point of censoring for purposes of analysis of efficacy outcomes. An indication of the occurrence is recorded on the daily post-op case report form (page 5) with more detail of the event, including specific cause of the event and status of the event (as described below) recorded on the competing event detail case report form (page 10). The patient may continue with the TransAeris therapy, if initiated, at the discretion of the clinician.

The event of interest is successful wean from mechanical ventilation and is classified as a Status=0 event. Death prior to successful weaning from mechanical ventilation is a competing event that precludes further weaning and would be classified as a Status=2, right censored event. Other events that hinder the event of interest and alter the probability of occurrence are classified as a Status=1, right censored event. This is depicted below in Figure 3: Competing Event Model.

[figure not shown]

Figure 3: Competing Event Model

The pre-specified competing events and censoring status are provided in Table 3, below. The events that would hinder weaning from mechanical ventilation are right censored with Status 1. Since an intact phrenic lower motor neuron is required for the stimulation to propagate through the diaphragm muscle, bilateral phrenic function, as identified by an observed EMG on both left and right hemidiaphragms, is necessary for the TransAeris stimulation to be effective. Lack of observed bilateral function, indicating a damaged phrenic nerve prior to or during surgery, is considered a competing event that would impede weaning with TransAeris. Additional right censor events may be considered that would meet the definition of precluding or impeding the event of interest (i.e. successful wean) from occurring.

Table 3: Competing Events

Event type	Censor Status	Description	Observed (Suarez-Pierre)
Desired Event	0	Successful wean	39.7%*
Right Censor	2	Death prior to wean, precludes event of interest	20%**

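### Section 8.4.2 does not require survival for a successful wean, and its fixed-window ventilation time scores a ventilated death at 24 h like a wean at 24 h (minor; reword)

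*Combined protocol and SAP*

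**What the plan says.** Section 8.4.2 (Primary Efficacy Endpoint) names two kinds of primary efficacy measure, each at 48 and 120 hours: mechanical ventilation (MV) time and the proportion successfully weaned.

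- **Wean.** "A wean will be considered successful if the patient is not reintubated within 48 hours of extubation". The proportion weaned comes from a cumulative incidence function (CIF).
- **MV time.** This is the "cumulative proportion of time on mechanical ventilation over the 48- or 120-hour period", counted from ICU entry. The only adjustment concerns a failed extubation: "If an extubation is attempted but is not successful (i.e., less than 48 hours"), that time is not treated as off the ventilator. The CIF is not named for this measure. The data "will be assessed using non-parametric techniques".
- **Competing events (section 7.5.1.4).** "Death prior to successful weaning from mechanical ventilation is a competing event", coded Status=2. Other events that hinder weaning "are classified as a Status=1, right censored event". The date and time of a competing event "will establish the point of censoring for purposes of analysis of efficacy outcomes".
- **Elsewhere.** Section 8.4.3 sets ventilator-free days (VFD28) to zero for a death within 28 days. Section 8.7 rules out imputation. Section 3.6.1, on when electrodes may be removed, speaks of a patient "successfully liberated from mechanical ventilation for 48 hours".

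**The concern.** Both primary measures should separate a patient who recovers from one who dies. As worded, neither does so reliably.

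The wean rule tests only for absence of reintubation. A patient who is extubated and dies soon afterwards cannot be reintubated and so passes. The MV share has a fixed denominator, so hours after death add nothing to the numerator and act as hours off the ventilator. VFD28 in the same plan takes the opposite view of death.

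Section 4.1 describes a population with high mortality and counts pilot patients as extubated successfully either within 30 days or before death, so an extubation followed by death is not a remote case. Two analysts could give the same patient different values on a primary endpoint. In an open-label study, the convention might then be chosen after the deaths are known.

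**Working it through.** The plan gives no figure of its own on this point, so there is nothing to reproduce. The check applies the wording to example patients and then sizes the effect. Event times are assumptions.

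**Inputs.** 30 subjects, half per group, so 15 per arm (sections 1 and 4.2). Positive predictive value 56.5% for ventilation of at least 24 h; on MV at 48 h and 120 h, 65.9% and 34.8% of those patients (section 4.2, Table 1).

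**1. Wean.** Take extubation at hour 40 and death at hour 44, with no reintubation.
- Literal 8.4.2: no reintubation within 48 h, so a successful wean.
- Status=2 requires death before successful weaning. If the wean already counts as successful, Status=2 does not apply; if it does not, it does. The definition decides, and it is silent on survival.
- Effect: 1/15 = 6.7 points of the raw proportion weaned per such patient. This is approximate, because the plan uses a CIF and earlier censoring changes the step. The documents give no rate for these deaths.

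**2. MV time.** Take a death on the ventilator at 24 h.
- Literal share: 24/48 = 50%; 24/120 = 20%.
- Successful wean at 24 h: 24/48 = 50%; 24/120 = 20%. The values are identical.
- If hours after death count as on the ventilator: 100% in both windows.
- Shift in the mean of an arm of 15: (1 − 24/48)/15 = 3.3 points; (1 − 24/120)/15 = 5.3 points.
- If the death time is instead uniform over 24–48 h (mean 36) or 24–120 h (mean 72): (1 − 36/48)/15 = 1.7 points; (1 − 72/120)/15 = 2.7 points.

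**3. Against the noise, 120-hour share.** Bands from section 4.2:
- weaned before 24 h: 43.5%
- weaned at 24–48 h: 0.565 × 0.341 = 19.3%
- weaned at 48–120 h: 0.565 × (0.659 − 0.348) = 17.6%
- on MV at 120 h: 0.565 × 0.348 = 19.7%

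With assumed shares of 0.1, 0.3, 0.7 and 1.0 the SD is 0.357. The standard error (SE) of a 15-v-15 difference is 0.357 × √(2/15) = 13.0 points. One death at 24 h is 5.33/13.0 = 0.41 SE. Moving the first band's share between 0.15 and 0.05 gives 0.43 to 0.39.

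**4. On ranks, since the plan is non-parametric.** A death at 24 h outranks 0.435 of the other arm if scored literally. Scored 100%, it outranks 0.803 + 0.197/2 = 0.902. The Mann-Whitney probability moves by (0.902 − 0.435)/15 = 0.031, against a null SE of √(31/(12 × 225)) = 0.107, about 0.3 SE.

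**5. Status=1.** Section 7.5.1.4 gives these patients a censoring point too. A censoring time is not a value for a share of a fixed window, so the text does not say whether ventilator hours after the event count.

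**The case against.** **The sensible reading is already implied.** The bracketed 48 hours in the failed-extubation rule, and the phrase in section 3.6.1, suggest that 48 hours of survival off the ventilator is meant. This makes that reading more likely but does not state it. The first sits in the rule for counting ventilator time, and the second concerns electrode removal.

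**Death is handled.** Deaths before a successful wean are Status=2, and section 7.5.1.4 sets a censoring point for efficacy outcomes. A reader might infer that the plan ignores death; it does not. What is missing is the status of a death soon after extubation, and a value for the MV share.

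**A literal value is still a value.** Observed hours over a fixed window can be computed, and other estimands are defensible. That stands, and is why the literal version should remain as a sensitivity analysis.

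**Stronger readings the documents do not support.**
- *The pivotal sample size is compromised.* Section 4.2 sizes that trial on the proportion on MV at 48 h. The patient extubated at 40 h and dead at 44 h is off MV at 48 h under either reading, and the control rate comes from external datasets.
- *The wording biases the result towards the device.* With deaths equal in number and timing between arms, no between-arm bias is expected, and the documents give no reason to expect a difference.
- *Status=1 events could swing the result widely.* The widest spreads arise only if observed ventilator hours after the event are discarded, although 8.4.2 counts time on the ventilator. Table 3's rates carry no timing for these events.

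**The effect is small.** That stands: the study is descriptive (section 8.3), section 4.2 expects it to be inconclusive, and mortality and VFD28 would show an excess of deaths.

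**Conclusion.** The point holds as a minor defect of wording with a clear remedy. Followed literally, 8.4.2 credits a death within 48 hours of extubation as a wean, and it gives a ventilated death at 24 h the same MV share as a wean at 24 h. No other section settles either case.

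The effect is at most a fraction of a standard error per patient on MV time. It rests on 15 per arm, an assumed death at 24 h (an earlier death would move the mean more) and assumed shares within the bands. How often deaths soon after extubation would occur cannot be sized from the documents. The Status=1 part is a clarification only. The reason to act is that the study is meant to inform the pivotal trial's design (section 8.1), and the rules are best fixed before any deaths are seen.

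**What to change.** 1. **Wean.** In 8.4.2: *A wean is successful if the patient is alive and has not been reintubated 48 hours after extubation.* In 7.5.1.4 and Table 3: *Death within 48 hours of extubation is death prior to wean, Status=2.*
2. **MV time.** In 8.4.2: *For a patient who dies before successful wean, the hours from death to the end of the window count as on mechanical ventilation; for a patient who dies after successful wean, the denominator stays 48 or 120 h and only observed ventilator hours count.* The second clause is needed: a patient weaned at 20 h who dies at 80 h would otherwise be 20/80 = 25% or (20 + 40)/120 = 50%, depending on the analyst. Under the rule the value is 20/120 = 16.7%. Report the literal observed-hours version as a sensitivity analysis, with the number and timing of deaths by arm.
3. **Status=1.** State one convention for the MV share, for example ventilator hours counted as observed. The choice is the sponsor's. Say that rules 2 and 3 replace the 7.5.1.4 censoring point for MV time only.

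**Cost.** A few sentences and no new data: MV start and stop times (Table 2a), competing-event times, daily forms and deaths (as serious adverse events) are already recorded. The downside is that MV time becomes partly a composite of ventilation or death and overlaps VFD28.

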8.4.3 Secondary Endpoints

Secondary endpoints are defined as follows:

- All-cause mortality through 30 days
- Mechanical Ventilation time, as the cumulative time on mechanical ventilation from ICU entry and paralytic reversal to successful wean,
- Ventilator-free days, defined(15) as time free from mechanical ventilation during first 28 days, where:
$$\begin{aligned} VFD28 &= (28 - \text{Time on MV}) \text{ if Time on MV is less than 28 days;} \\ &= 0 \text{ if Time on MV} \geq 28 \text{ days} \\ &= 0 \text{ if death within 28 days} \end{aligned}$$
- Hospital length of stay (admission to discharge)
- ICU length of stay
- Change in median frequency and total power of the power density spectrum (PSD) analysis of inspirations at baseline, pre-stimulation, and post-stimulation in cross-over control patients

All endpoints will be summarized and reported descriptively to characterize outcomes. No *a priori* hypothesis testing is planned for this study.

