The STS performance measures include a quality performance measure (NFQ #0129) for prolonged mechanical ventilation (PMV), defined as the need for intubation greater than 24 hours. The STS and other published data on this study population will provide the basis for comparison of the observed feasibility of safety and efficacy and thus determine the progression to a randomized controlled pivotal study. Current literature(11,12) on PMV illustrates the need for a therapy and identifies that an “enriched study population” based on the risk for PMV may be the most suitable target for an intervention(12).

The initial investigation of TransAeris (IDE G150040) also enrolled in a surgical population. That investigation was primarily focused on placement, stability and removal of the TransLoc electrode during and after the surgical procedure. That study was able to enroll rapidly (twelve patients in under eight weeks) and demonstrated the successful placement, stability and removal of the electrodes in the surgical population.

The next investigation of TransAeris (IDE G170294) focused on enrollment in an “enriched study population” undergoing an open sternotomy cardiac surgery. In this enriched population, meeting identified risk factors for PMV, it was anticipated that the study would provide an apparent visibility to potential benefit. There were 32 patients implanted in this study, 10 received experienced PMV and received TransAeris stimulation. There were no device or procedure related serious adverse events reported in any of the patients. The risk factors for PMV identified five specific criteria that are able to further enrich the study population. Although there is a high incidence of complications and mortality in the targeted high-risk cardiac surgery patient group the patients in this study appeared to benefit from the TransAeris stimulation. Overall, there were

eight of ten patients that received TransAeris stimulation who were successfully extubated within the 30 days or prior to death. At 48 hours post-op, there were 60% of the stimulated patients weaned and at 120 hours there were 70% weaned.

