8.2 General Considerations

Continuous data will be summarized using descriptive statistics: mean, standard deviation, median and interquartile range. Categorical variables will be summarized using frequency counts and percentages. For events which can occur more than once in a single subject (e.g., adverse events), the primary analysis will be based on the count of subjects experiencing the event; both patient and event counts will be reported.

All statistical analyses will be performed in STATA version 13.1 or later, or other widely accepted statistical analysis software packages.

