8.7 Handling of Missing Data

Every effort will be made to reduce the incidence of missing data. The study will be conducted with proper screening of study subjects, complete training of participating investigators, study coordinators and monitors. All subject data that are available on subjects who drop out during the study will be included. Missing data will not otherwise be replaced or otherwise imputed, as the primary analysis is to be conducted on the ICH E9 definition of the full analysis set.

The number and proportion of subjects eligible for and compliant with each follow-up examination will be presented. Subjects who withdraw from the study will be tabulated with reasons for withdrawal.

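### Secondary ventilation time in section 8.4.3 has no rule for patients who die unweaned or are still ventilated at day 30, and the mean/median summary in 8.2 cannot use their censored times

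*Combined protocol and SAP*

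**What the plan says.** - Section 8.4.3 ends the interval at weaning: "Mechanical Ventilation time, as the cumulative time on mechanical ventilation from ICU entry and paralytic reversal to successful wean". In the same list, ventilator-free days are given explicit values for death within 28 days and for 28 or more days of ventilation. Ventilation time is given neither.
- Section 8.2 fixes the summary: "Continuous data will be summarized using descriptive statistics: mean, standard deviation, median and interquartile range".
- Section 7.5.1.4 says that the date and time of a competing event "will establish the point of censoring for purposes of analysis of efficacy outcomes", and that death before weaning "would be classified as a Status=2, right censored event". Its Table 3 also right-censors, as Status=1, events that hinder weaning, such as sepsis, new dialysis and reoperation. It has no entry for a patient who is simply still ventilated at day 30.
- Section 8.4.2 assigns the competing-risk method to one quantity only: "The proportion weaned will be derived from the cumulative incidence function (CIF) of a competing risk analysis". Secondary ventilation time is not named.
- Section 8.7 states: "Missing data will not otherwise be replaced or otherwise imputed".
- Section 7.3 compares the arms over the first 120 hours. Over the 30-day period it compares ventilation time in all patients with the literature. Section 8.1 uses the data to set the parameters of the pivotal trial.

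**The concern.** The plan expects patients without a wean time. Table 3 cites about 20% for the row "Death prior to wean, precludes event of interest", and section 4.1 reports "eight of ten patients that received TransAeris stimulation who were successfully extubated within the 30 days or prior to death" in the pilot, so 2 of 10 were not. For these patients the definition in 8.4.3 has no end point, and the analyst must choose between two obvious defaults. One is to summarise only those who weaned. The other is to enter the time to death as if it were a completed time. Under the first, the summary describes how long weaning took in those who succeeded. Under the second, an early death counts as a short course of ventilation. Both make ventilation time look shorter than it was for the group as a whole.

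At stake are the comparison with literature in 7.3, any description by arm, and the pivotal-trial inputs in 8.1. Section 4.2 names reduced time on the ventilator as the intended outcome of the device, so this figure is likely to be read.

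**Working it through.** **1. Plan figure reproduced.** The plan gives no expected value for this endpoint. The nearest figure is section 4.2's expectation of 2 to 3 of 15 controls still ventilated at 5 days. With PPV 13/23 = 0.565 and 34.8% on the ventilator at 120 h (Table 1): 15 × 0.565 × 0.348 = 2.95, which agrees.

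**2. Patients affected.** Table 3's 20% is an approximate 96-hour predicted mortality from a cited cohort with prolonged ventilation, so it is applied to that share of each arm: 15 × 0.565 × 0.20 = 1.7. If it applied to all 15, the count would be 3.0. Survivors still ventilated at day 30 would add to this; the plan gives no figure for them.

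**3. Illustrative weaning curve.** Proportion still ventilated, from the plan's control inputs:
- 24 h: 0.565
- 48 h: 0.565 × 0.659 = 0.372
- 120 h: 0.565 × 0.348 = 0.197

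Assumption: constant hazard within each interval, and after 48 h a hazard of ln(0.659/0.348)/72 = 0.0089 per hour, carried on past 120 h. Fifteen patients placed at the probabilities (i − 0.5)/15 have times of 1.4, 4.4, 7.7, 11.2, 15.0, 19.2, 23.9, 31.0, 39.3, 49.7, 72.4, 100.7, 138.6, 196.2 and 320.1 h. The sum is 1030.8 h, the mean 68.7 h and the median 31.0 h.

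**4. Let the two longest fail** (close to 1.7):
- Left out: 514.5/13 = 39.6 h; median 23.9 h.
- Counted to an assumed death at 96 h: (514.5 + 2 × 96)/15 = 47.1 h; median 31.0 h.
- Ranked worst: median 31.0 h, unchanged, because 8 of 15 still weaned by 31.0 h.

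**5. Range in a large sample on the same curve** (mean 71.2 h and median 31.0 h with no failures; times capped at 720 h). The first figure in each pair takes failure as unrelated to duration; the second takes the longest-ventilated patients as the failures. Time to death is assumed to lie evenly between 24 and 96 h.

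| Failing, of patients ventilated ≥ 24 h | Left out: mean | Left out: median | Counted to death: mean | Counted to death: median |
|---|---|---|---|---|
| 10% | 68.4 to 53.2 | 28.3 to 27.9 | 67.3 to 53.6 | 30.5 |
| 20% | 65.5 to 43.0 | 25.3 to 25.0 | 63.7 to 44.9 | 30.2 to 30.1 |

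At 20%, leaving failures out lowers the mean by 5.7 h (71.2 − 65.5) to 28.2 h (71.2 − 43.0), and the median by about 6 h. Counting to death lowers the mean by 7.5 to 26.3 h and barely moves the median.

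**6. Conflict over Status=1 events.** Take a hypothetical patient with sepsis on day 2 who weans on day 10. Section 8.4.3 gives 10 days. The censoring rule in 7.5.1.4 stops the clock at 2. Both cannot apply to the same endpoint.

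**The case against.** The strongest reply is that nothing in the plan excludes these patients. Section 8.3 analyses all available data from all enrolled subjects, start and stop times of ventilation are collected for everyone (Table 2a), and 7.5.1.4 gives death a censoring time for efficacy outcomes in general. The no-imputation rule in 8.7 concerns missing data, whereas death before weaning is an observed, dated event. This stands: a reader might infer that failures have no value and must drop out, but the documents do not say so. It does not close the gap, because a censored time still cannot enter the mean or median prescribed in 8.2.

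A reader might also infer that the arm with more failures will be made to look better. That needs a between-arm comparison of full-course ventilation time, and 7.3 plans the comparison of arms for the first 120 h only. Excess failures would also show elsewhere. Ventilator-free days score death as 0: in the 15-patient illustration the mean falls from 25.1 to 22.8 days with two failures. Thirty-day mortality is reported separately. No hypothesis test rests on the endpoint.

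Large between-arm distortions can be produced, but they are mostly convention. Assume 20% of prolonged-ventilation controls and 10% of such treated patients fail, using the plan's 48 h figures, 34.8% and 30% on the ventilator at 120 h, and an assumed tail beyond that. Scoring failures at 720 h turns a mean difference of 36.9 h into −1.4 h once they are left out, a shift of 38.3 h. Scoring them at 96 h instead, the shift is 3.0 h, or 1.2 h if failure is unrelated to duration. With the failure rates reversed it is 4.4 or 2.8 h. The unequal failure rates are themselves assumed.

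**Conclusion.** The concern holds as a gap in the definition and a mismatch between sections. Section 8.4.3 gives secondary ventilation time no rule for death before wean or for no wean by day 30, and the summary in 8.2 does not fit the censoring in 7.5.1.4. Each of the two default ways of filling the gap shortens the mean; leaving failures out also shortens the median. About 1.7 of 15 patients per arm are expected to be affected, given the plan's 20% and PPV of 56.5%. The size in hours is not fixed by the documents: it rests on the assumed tail, on when deaths occur, and on whether the longest-ventilated patients are the ones who fail. The direction holds in every case tabulated.

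The documents do not support saying that unweaned patients will be excluded, or that the plan's comparison of the arms will be reversed. The point is minor: the endpoint is secondary and descriptive, and ventilator-free days and mortality are reported alongside it.

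**What to change.** In section 8.4.3, state one rule for all patients in the analysis set, by arm. Either:

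- estimate the cumulative incidence of successful wean to day 30, with death before wean as a competing event and patients still ventilated at day 30 censored there, and report the times at which it reaches 25%, 50% and 75% where reached; or
- rank death before wean and not weaned by day 30 as the worst outcome, and report median and IQR only.

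With either rule:
- report by arm the number who died unweaned and the number still ventilated at day 30;
- label any mean taken in weaned patients only as such;
- state how Status=1 events enter this endpoint, so that 7.5.1.4 and 8.4.3 agree;
- note that results by arm after 120 h include control patients who crossed over to stimulation.

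The cost is a few lines of text and no new data, since ventilation times, deaths and competing events are already collected. The downside is that a mean in hours is no longer the headline summary.
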